#### b. Drugs to be used (dose, method, schedule of administration, dose modifications, toxicities), include Toxicity Grading Scale (if applicable)

The study will not involve additions or changes to therapeutic medication regimens.

#### c. Devices to be used

## ACCOMPANEERS STUDY DETAILED PROTOCOL

The study will not involve additional medical devices.

**d. Procedures / surgical interventions, etc.**

The study will not involve additional procedures or surgical interventions.

**e. Data to be collected and when the data is to be collected**

Data collection will be conducted by trained study staff that are independent of the patient's health care providers and clinical care. An enrollment questionnaire will be administered at the time of study enrollment (see attached Enrollment Form). Questionnaires related to medication adherence will be administered by study staff prior to study initiation and every three months thereafter until study completion (see attached Adherence Questionnaire, and translated version). Study staff will also conduct assessment of hemoglobin A1c, and systolic and diastolic blood pressure during these visits. Hemoglobin A1c will be assessed using fingerprick point-of-care technology, which gives an immediate result in the patient's presence. Data will be immediately transferred to data collection forms, then deleted from data collection devices and collection strips used to collect blood will be discarded in the patient's presence. No blood samples will be stored or transported as part of this study. These assessments and interviews will take place in the participant's home or the clinic, according to the participant's preference.

The study will involve collection of data from the medical record, which will be achieved by the use of unique patient identifiers linking to medical record numbers. Chart reviews will be conducted by study staff, and will be limited to those data specified in data collection forms (see attached Medical Records Form). No additional data will be collected from the medical record.

Questionnaires related to health beliefs, health literacy, and satisfaction with medical care will be conducted at baseline and at three month intervals after study initiation among selected patients by study staff (see attached Qualitative Supplement, and translated version).

### **VI. BIOSTATISTICAL ANALYSIS**

**a. Specific data variables being collected for the study (e.g. data collection sheets).**

All study data will be collected using data collection sheets (see attached, per above).

Primary study outcomes:

- Self-report of medication adherence, as derived from study questionnaires adapted from validated measures.

Secondary study outcomes:

- Proportion of scheduled monthly chronic disease appointments attended in preceding three months.
- Systolic and diastolic blood pressure (hypertension patients)
- Hemoglobin A1c (diabetes patients)
- PHQ-9 scores (patients with depression)
- Qualitative assessments of patients' health beliefs, health literacy, and satisfaction with medical care

**b. Study endpoints**

Study timeframe: The study, including the enrollment period and baseline data collection, will run for approximately 44 months in total. Baseline data collection and participant enrollment will occur concurrently prior to study initiation; this period is anticipated to take approximately one month. The study will then run for the subsequent continuous 21 months in the original communities, then conclude. Upon completion of data collection in the original four communities ("A" – "D"), baseline data collection and participant enrollment in the four remaining communities ("E" – "H") will commence; this period is expected to take approximately one month. Thereafter, the study will run in these communities for the subsequent continuous 21 months.

## ACCOMPANEERS STUDY DETAILED PROTOCOL

### c. Statistical methods

Patients will be categorized as having adequate adherence based on pre-determined cutoff points from the standardized assessments. Hypertensive patients with a systolic blood pressure of <140 mmHg and a diastolic blood pressure of <90 mmHg (<130 mmHg and <80 mmHg, respectively, in patients with comorbid diabetes), and diabetic patients with a hemoglobin A1c of less than 7.0% will be defined as having achieved disease control. The stepped wedge crossover study design allows for pre- and post-intervention comparisons with the added benefit of accounting for time-related bias. Due to the small number of communities and expected variation in the number of participants per community, we will use random-effects generalized estimating equations with “sandwich” variance estimates to conduct individual-level analyses adjusted for clustering at the community and individual levels.

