## ACCOMPANEERS STUDY DETAILED PROTOCOL

Aim 2. Assess the impact of a CHW intervention on scheduled clinic visit attendance for patients with diabetes, hypertension and depression  
Aim 3a. Assess the impact of a CHW intervention on changes in Hb A1c in diabetic patients  
Aim 3b. Assess the impact of a CHW intervention on changes in systolic and diastolic blood pressure in patients with hypertension  
Aim 3c. Assess the impact of a CHW intervention on changes in Patient Health Questionnaire-9 (PHQ-9) scores among patients with depression  
Aim 4. Assess health beliefs, literacy, and satisfaction with medical care among patients participating in a CHW intervention.

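### Does Section VI.c replace the measured A1c and blood pressure of Aims 3a and 3b with a yes/no control variable?

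*Combined protocol and SAP*

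**What the plan says.** Section II.a states Aim 3a as "Assess the impact of a CHW intervention on changes in Hb A1c in diabetic patients" and Aim 3b as "Assess the impact of a CHW intervention on changes in systolic and diastolic blood pressure in patients with hypertension". The secondary outcomes in Section VI.a repeat the same three measurements, for the hypertension and diabetes groups respectively, and do not mention disease control. Section V.e provides for their collection at the three-monthly visits: "Study staff will also conduct assessment of hemoglobin A1c, and systolic and diastolic blood pressure during these visits".

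Section VI.c first says that adherence will be split at preset cutoffs. It then defines disease control. The pressure part begins "Hypertensive patients with a systolic blood pressure of <140 mmHg and a diastolic blood pressure of <90 mmHg", with a lower pair of limits (130 and 80 mmHg) for patients who also have diabetes. The A1c part reads "diabetic patients with a hemoglobin A1c of less than 7.0% will be defined as having achieved disease control". The section closes with one sentence proposing generalized estimating equations with sandwich variances "to conduct individual-level analyses adjusted for clustering at the community and individual levels". That sentence names no outcome, distribution or link. The power statement in Section VI.d concerns adherence only.

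**The concern.** A reader who goes straight to Section VI.c finds one variable built from A1c and one built from blood pressure, both binary. They sit next to a dichotomised primary outcome and just before the model. It is natural to infer that control is what will be modelled.

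If so, the result would be a change in the share of patients below a cutoff, not the changes in A1c and pressure that Aims 3a and 3b name. The pressure rule requires both components to be below their limits, so it gives one result where Aim 3b names two. A binary version of a continuous measurement also usually carries less information. If both versions were run with neither marked as the main one, the emphasis could be chosen after the results were known.

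**Working it through.** **Step 1: the texts side by side.**

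| Place | A1c and blood pressure | Disease control |
|---|---|---|
| II.a, Aims 3a and 3b | Changes in the measurements | Not mentioned |
| V.e | Measured at the three-monthly visits | Not mentioned |
| VI.a, secondary outcomes | Listed as measurements | Not mentioned |
| VI.c | Appear only as inputs to the cutoffs | Defined, no role given |
| VI.d | Not mentioned | Not mentioned |

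Three places name the measurements and one defines control. None says that control takes their place. A category needs a written cutoff; a reading in mmHg or percent does not. Silence in VI.c about the measured values is therefore weak evidence that they were dropped. PHQ-9 scores and clinic attendance are secondary outcomes in VI.a and are not mentioned in VI.c at all, yet nobody would conclude that they will not be analysed. Control is also computed from the recorded readings, so defining it removes no data.

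**Step 2: what a replacement would cost.** The protocol has no figure to reproduce: it gives no mean, SD, correlation or control rate for A1c or pressure. Every input below is an assumption. The calculation uses independent observations, not the clustered, repeated stepped-wedge data.

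*A1c, single cutoff.* For a normal measurement, a small shift and a proportion p controlled, the ratio of observations needed (binary to mean) is p(1−p)/φ(z_p)².

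- p = 0.5: 0.25/0.3989² = 1.57
- p = 0.3: 0.21/0.3477² = 1.74
- p = 0.2: 0.16/0.2800² = 2.04

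*Pressure, joint rule.* Assumed: bivariate normal, SD 18 systolic and 11 diastolic, correlation 0.6, fall of 5/2.5 mmHg, 80% power, two-sided 5%.

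- Mean systolic: n per group = 2(1.960 + 0.842)² × 18²/5² = 203.4, so 204.
- Mean diastolic: 2(1.960 + 0.842)² × 11²/2.5² = 303.9, so 304.
- Control, two proportions: n = [1.960√(2p̄(1−p̄)) + 0.842√(p₁(1−p₁) + p₂(1−p₂))]²/(p₂−p₁)², where p̄ is the average of p₁ and p₂.
- Below 140/90, from mean 140/85: control goes from 0.4285 to 0.5389, n = 321.
- Below 130/80, from mean 145/85: control goes from 0.1359 to 0.2058, n = 454.

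| Rule | Against systolic (204) | Against diastolic (304) |
|---|---|---|
| Below 140/90 | 321/204 = 1.57 | 321/304 = 1.06 |
| Below 130/80 | 454/204 = 2.23 | 454/304 = 1.49 |

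With the correlation at 0.4 or 0.8, the ratios under the 140/90 rule are 1.48 or 1.64 against systolic and 0.99 or 1.10 against diastolic. Under the 130/80 rule they are 2.26 or 2.16 and 1.52 or 1.45.

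The loss is thus real for A1c and for systolic pressure, and close to nil for diastolic pressure under the 140/90 rule. The 130/80 rule, with the larger ratios, applies only to patients with both conditions.

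**Step 3: does the loss arise?** Only if control is analysed instead of the measurements. Step 1 finds nothing that says so. If the measurements are modelled and control is reported beside them, every ratio in Step 2 is irrelevant.

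**The case for a change.** The strongest argument for a change is that a variable defined in the statistical methods section is presumably meant to be analysed, and that VI.c gives the measured values no model of their own. Two competent analysts could follow the text and lead with different results, one with a mean difference and one with a percentage controlled. With only eight communities, precision should not be given away, and a clarifying sentence would be cheap because the readings are already taken.

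Part of this stands. The role of control is not written down, the adjacent treatment of adherence invites the other reading, and a line settling it would do no harm. It is also true by construction that one joint rule cannot show systolic and diastolic changes separately.

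The rest carries less weight. Room for selective emphasis is limited because control is absent from both the aims and the outcome list: an analyst who led with it would be leading with an unlisted outcome. The missing outcome and link are a general feature of the single model sentence and apply equally to adherence, attendance and PHQ-9. Naming a link for A1c and pressure alone would not complete their model either, because VI.c speaks of accounting for time-related bias without writing a time term.

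**Conclusion.** The concern does not call for a change. The textual observation is correct: control is defined without a role, and the model sentence names no outcome. But the aims and the secondary outcome list already fix measured A1c, systolic pressure and diastolic pressure as what Aims 3a and 3b are about. An analyst following them would estimate a difference in each measurement and report the proportion controlled as a supporting, clinically readable summary. That is a sound analysis of the stated aims.

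On that reading the loss is zero. If control were substituted, the cost would be about 1.6 to 2.0 times the observations for A1c with 50% to 20% controlled. For pressure it would be about 1.5 to 2.3 times against systolic and 1.0 to 1.5 times against diastolic. Those figures rest wholly on assumed means, SDs, correlations, falls and control rates, and on independent observations, so they illustrate the loss without measuring it for this design. The outcomes are secondary, and the adherence power statement is unaffected.

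The conclusion would change only if some other trial document named control as the analysed outcome in place of the measurements. The attachments were not available, but VI.c does not refer to them on this point.

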#### c. Treatment assignment, and randomization (if applicable)

Please see Schema (attached) for visual explanation of study procedures.

Randomization: All communities will receive CHW accompaniment programs, but will be randomized at the community level in the order of program rollout. At present, CES only has the capacity to roll the Accompaneers program out to new project villages once every three months. Accordingly, prior to study commencement the order of rollout of the Accompaneers program to each of the project villages (Communities "A" through "D") will be assigned at random. Following data collection in the first four study communities, the remaining four communities will be randomized (Communities "E" through "G").

Patient enrollment in Accompaneers program (specific to enrollment in program, not in research study): When the Accompaneers program is introduced to a community, all eligible patients will be offered the option of participation in the program. Those accepting participation will be introduced to an Accompaneer in the clinic, and program home visits will commence in the week following enrollment.

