### d. Power analysis (e.g. sample size, evaluable subjects, etc)

With an average of 32 patients per community with diabetes or hypertension across the eight study communities, an 80% participation rate, and eight data collection periods per community (baseline, 3 months, 6 months, 9 months, and 12 months), we will have greater than 80% power to detect a 40% change in adherence, assuming a 50% of individuals meet the definition of good adherence prior to the intervention. These estimates are intentionally conservative, with lower baseline rates of adherence, greater improvements in adherence, and greater program participation observed in our pilot community.

With 50 patients with depression total in communities “E”–“H”, utilizing a paired t-test, and anticipating a baseline adherence of 50%, we will have 90% power to detect a 40% improvement in adherence, an effect similar to that seen in the preliminary results from communities “A” – “D”.

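### The plan uses a sandwich variance because there are few communities, but names no small-sample correction or reference distribution; in its ordinary community-level form the adherence test would reject about 14-22% of the time under no effect

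*Combined protocol and SAP*

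**What the plan says.** Section VI.c chooses the method in one sentence, which begins "Due to the small number of communities and expected variation in the number of participants per community, we will use random-effects generalized estimating equations". The second half of that sentence adds the variance and the level of analysis: "with “sandwich” variance estimates to conduct individual-level analyses adjusted for clustering at the community and individual levels". It gives no small-sample correction, degrees of freedom, reference distribution, significance level or working correlation, and does not say at which level the sandwich is formed. No other section supplies these, and the attachments listed in section XI do not include a separate analysis plan.

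The primary outcome in section VI.a is "Self-report of medication adherence, as derived from study questionnaires adapted from validated measures". Under section IV.c, communities "will be randomized at the community level in the order of program rollout", in two sets of four, the second set after data collection in the first. Section VI.d counts patients "across the eight study communities" and states "we will have greater than 80% power to detect a 40% change in adherence". It gives no intraclass correlation (ICC).

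Two related passages do not agree. Section IV.c labels the second set of four E to G, while section VI.b, on "baseline data collection and participant enrollment in the four remaining communities", labels it E to H. Section VI.d bases the depression power on a paired t-test, which section VI.c does not mention.

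**The concern.** The stated reason points the wrong way. A sandwich variance is justified when independent clusters are many. With few, the residuals it is built from are too small, because the model was fitted to the same few communities, so the standard error is biased downward. It is also noisy, so a normal reference is too generous. Eight randomised communities call for a correction.

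If none is applied, the interval for the primary outcome is too narrow, and a chance result would be called an effect about three to four times as often as a 5% test allows. The programme continues locally whatever the result (section I.b), but section I.c expects the findings to inform adoption at other sites. Section VI.d also shows that preliminary results from A to D have been seen, so a method left open could be chosen with knowledge of the data.

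**Working it through.** **Inputs from the documents.** Eight communities in two sets of four; 32 x 0.80 = 25.6 patients per community, about 205 in all; baseline adherence 50%; one new community every three months; eight data rounds stated in VI.d but five time points listed (both were run).

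**Assumed, because the documents do not say.** Two-sided 5%; crossover of one community per round from the second round (the Schema is not in the text); community sizes of about 14-38. Standard deviations on the logit scale: community 0.2-0.8, community-by-round 0-0.4, patient 1.0-1.5.

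**The plan's own figure.** Reading 40% as relative (0.50 to 0.70), a two-proportion test has 83.5% power with 102 v 102 and 98.7% with 205 v 205. The stepped-wedge weighted least-squares variance with a normal reference gives 84-99% for ICC 0.01-0.10, and 68-76% at ICC 0.20 with cluster autocorrelation 0.8. So the claim of more than 80% is met under most assumed ICCs.

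**Why the test inflates.** The community-level sandwich is V = A⁻¹(Σ UₖUₖ′)A⁻¹, summed over k = 1 to 8, with Uₖ the score of community k. In simulation its mean SE was about 70-80% of the true SD of the estimate. Treating the SE as fixed at a fraction r of the truth, rejection under no effect is 2[1 - Φ(1.96r)]:
- r = 0.70: 2[1 - Φ(1.372)] = 17.0%
- r = 0.80: 2[1 - Φ(1.568)] = 11.7%

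Variation of the SE from trial to trial adds to this.

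**Simulated rejection under no effect, community-level sandwich, eight communities.**

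| Test | Rejection |
|---|---|
| Uncorrected, normal, round effects shared by both sets | 14-18% |
| Uncorrected, normal, round effects separate per set | 17-22% |
| Scaled by K/(K - 1), normal | 12-20% |
| Uncorrected, t on 6 df | 7-14% |
| Kauermann-Carroll, normal | 9-13% |
| Kauermann-Carroll, t on 6 df | 4.5-7.3% |
| Mancl-DeRouen, normal | 4-9% |
| Mancl-DeRouen, t on 6 df | 1-4% |
| Permutation over 24 x 24 = 576 orders | 4.3-5.2% |

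The uncorrected rows come from simulations with separately chosen variances, 1,000 to 3,000 replicates per setting (simulation error about 0.7-1.2 points at 18%). Five or eight rounds gave practically the same range. The rate depends little on the assumed variances: with community SD 0.2 and no round variation it was still 15.9% (shared) and 17.5% (separate).

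**Mixed-model reading, model-based SE, normal reference.** Logistic: 6-7% at community-by-round SD 0-0.2, and 14% at 0.4. Linear: 5-14%, or 4-6% with a community-by-round term.

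**Cost of correcting, eight communities.** The t reference alone widens intervals by 2.447/1.96 = 1.25. With the variance correction the total is about 1.6 (nested working correlation: half-width 10-13 percentage points instead of 6-8). Power for 50% to 70%, corrected t test with nested correlation:
- community-by-round SD up to 0.4: 83-97%
- SD 0.5: 77%
- SD 0.7: 64%
- SD 1.0: 46%

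With independence working correlation it was about 62% in one setting.

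**Depression, E-H only.** 50/4 = 12.5 patients per community. The same rule gives 4 - 2 = 2 df, critical value 4.30, and 4! = 24 orders, so the smallest permutation p is 1/24 = 0.042. Power of the corrected t test for 50% to 70% was about 15-20% in the settings run, against 90% in VI.d.

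**The case against.** The strongest reply is that the plan does not commit to the ordinary community-level form. The 14-22% needs that level, no correction, a normal reference, a 5% level and a set of variances, none of which the documents state. *Random-effects* may mean a mixed model, which stays near nominal when communities vary little between rounds. This stands: the certain defect is that the test is under-specified, and the inflation is conditional. But the sentence names a sandwich, gives few communities as its reason, and mentions no remedy, so the ordinary form is a natural way to carry it out.

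A reader might go further and infer that a person-level sandwich with independence correlation is allowed, with error rates of 31% or more. The documents do not support that. Section VI.c requires adjustment for clustering by community as well as by person, and that analysis makes no adjustment for community.

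It can also be said that permutation is the better primary test, since in these runs it was closer to 5% and had somewhat more power (90-99% against 83-97%, at community-by-round SD up to 0.4). That is a fair preference. The corrected GEE is proposed as primary because one model then gives the estimate, interval and p-value. The reverse is acceptable if one is named in advance.

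**Conclusion.** The concern holds in conditional form and should be fixed before analysis. The omission is certain from the text. If the sandwich is formed at community level, uncorrected, with a normal reference, the eight-community adherence test rejects about 14-22% under no effect at a nominal two-sided 5%. This rests on assumed variances and an assumed crossover schedule, but mainly reflects the number of communities, which the documents do give. Under a mixed model the rate is about 5-7%, or about 14% with community-by-round SD 0.4.

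Three stronger conclusions are not supported: that the team has planned an inflated test; that the stated power for diabetes and hypertension is wrong; and that the eight-community remedy carries over to depression in E-H. Secondary outcomes were not simulated.

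**What to change.** For the eight-community analysis, add to section VI.c:
1. Tests are two-sided at 5%.
2. The GEE contains intervention status, round effects separate for each set of four, and a working correlation with person and community terms.
3. The primary test uses a community-level sandwich with Kauermann-Carroll correction and a t reference on communities minus 2, that is 6, df.
4. A permutation test over the 576 within-set orders is a sensitivity analysis, with weights estimated without the intervention term (with it, rejection reached 6.0%).
5. State whether *random-effects* means this GEE or a mixed model.

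Correct the E to G label in section IV.c to agree with E to H in section VI.b, because the 6 df and the 576 orders need eight communities.

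For depression in E-H, state separately which analysis applies, restate the power for that analysis, and treat a community-randomised test in those four communities alone as having little power.

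The change needs wording and a few lines of code, and no new data. The cost is the wider intervals, and power above 80% for 50% to 70% only with the nested working correlation and community-by-round SD up to about 0.4.

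### Section VI.c claims that the stepped wedge handles time-related bias, but the model it states adjusts only for clustering and names no period or wave term

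*Combined protocol and SAP*

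**What the plan says.** Section VI.c (Statistical methods) says that the stepped wedge design "allows for pre- and post-intervention comparisons with the added benefit of accounting for time-related bias", and attaches a stepped-wedge methods reference to that sentence. It then gives the model: a random-effects GEE with sandwich variance, "to conduct individual-level analyses adjusted for clustering at the community and individual levels". No section names a round, calendar-time or wave term, a coding of exposure, or a way to combine the two waves.

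The surrounding design is set out as follows.

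- Section IV.c randomises the order of rollout by community, because "CES only has the capacity to roll the Accompaneers program out to new project villages once every three months". It adds: "Following data collection in the first four study communities, the remaining four communities will be randomized". E-H are therefore a second, separately randomised wave.
- Section V.e has adherence measured "prior to study initiation and every three months thereafter until study completion".
- Section VI.b says of A-D: "The study will then run for the subsequent continuous 21 months in the original communities, then conclude". E-H then run for a further 21 months.
- Section VI.d gives "eight data collection periods per community (baseline, 3 months, 6 months, 9 months, and 12 months", which says eight but lists five. It calculates depression power "utilizing a paired t-test, and anticipating a baseline adherence of 50" percent.

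**The concern.** Clustering adjustment and a sandwich variance act on weights and standard errors. They do not take a time trend out of the point estimate. In a stepped wedge, exposure rises with calendar time by construction, so the protection that VI.c claims comes from time terms in the mean model. Without them, the primary adherence result and the quantitative secondary outcomes mix the programme effect with whatever else changed over the same months. An improving background would be credited to the programme, and a worsening one would hide part of its effect.

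The documents give some reason to expect change. Section I.b describes clinics being rehabilitated and staffed, and patients found by screening who have been put on treatment. Section III.a admits patients on raised blood pressure or a raised PHQ-9, which invites regression to the mean in those two outcomes.

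The waves may also differ. Section I.b says that six communities were served at the start and four joined later. If A-D come from the original six, at most two of E-H do, so at least two of E-H joined after the study began. Their trends need not match those of A-D.

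**Working it through.** **1. The plan's own figure.** Section VI.d states more than 80% power for a 40% change from 50% adherence. It gives no alpha, ICC or formula, and does not say whether 40% is relative, so no unique figure can be reproduced. Take 50% to 70%, two-sided 5% (assumed) and 32 × 8 × 0.80 = 204.8 patients, or 102 per arm. The null SE is √(2 × 0.6 × 0.4 / 102) = 0.0686 and the alternative SE is √((0.25 + 0.21) / 102) = 0.0672. Power is Φ((0.20 − 1.96 × 0.0686) / 0.0672) = Φ(0.98) = 0.84. This unclustered figure agrees with the stated bound but has no time term.

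**2. Rounds.** Quarterly surveys over 21 months give 21/3 + 1 = 8 rounds, numbered 0 to 7. The five listed time points were run as a variant.

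**3. Timing gap.** A community exposed from round k has mean exposed round (k + 7)/2 and mean unexposed round (k − 1)/2. The difference is 4 rounds = 12 months, and 12/21 = 57%. This holds for every k, so it does not matter whether the first rollout follows the baseline or the month-3 survey. Exposed and unexposed communities coexist in only three rounds per wave.

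**4. Share of drift absorbed.** Generalised least squares was applied to community-round means: two waves of four communities, 25.6 patients each, exchangeable correlation, both rollout schedules. ICC (0.01-0.20) and within-patient correlation (0-0.5) are assumed.

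- Without time terms, a drift of 1 point per round gives a spurious effect of 3.87 to 3.99 points. A 10-point rise over 21 months is 10/7 = 1.43 points per round, so 3.87 × 1.43 = 5.5 and 3.99 × 1.43 = 5.7 points, or 55-57%.
- With the five listed time points, the same drift gives 3.1-3.6 points. The within-community ceiling is 2.5 rounds × 1.43 = 3.6.
- With wave-by-round terms it is 0.
- With an independence working correlation, the pooled gap of 3.64-3.68 rounds gives 52-53%.

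**5. False-positive rates, like for like.** These come from simulated trials with no true effect: binary outcome, 26 patients per community, ICC 0.05, within-patient correlation 0.3, identity-link exchangeable GEE clustered by community.

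| Variance | Drift | No period terms | Wave-by-round terms |
|---|---|---|---|
| Uncorrected sandwich | none | 10-11% | 17-18% |
| Uncorrected sandwich | 10-point rise | 76-80% | 16-17% |
| Mancl-DeRouen | 10-point rise | 68-72% | about 4% |

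**6. Price of the time terms.** With eight rounds the variance ratio is 3.10-3.85, so the SE ratio is √3.10 = 1.8 to √3.85 = 2.0. Power for 50% to 70% in diabetes and hypertension, with values using t on 6 df in brackets where available:

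- Community autocorrelation 1: 96% or more with eight or five rounds. For example, an SE of 4.1 points gives Φ(20/4.1 − 1.96) = Φ(2.92), above 99%.
- Eight rounds, ICC up to 0.10, zero within-patient correlation: 92% (79%) at worst.
- Eight rounds, ICC 0.20, autocorrelation 0.8, zero within-patient correlation: 83% (68%).
- Five rounds, ICC 0.10-0.20, autocorrelation 0.8, zero within-patient correlation: 76-87% (61-73%).

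**7. Gradual effects.** Let the effect reach 20 points in equal steps, and take as truth the mean over exposed community-rounds. For two steps with rollout after baseline, 8 of 44 exposed cells are at 10 points and 36 at 20, giving 800/44 = 18.2. With wave-by-round terms (ICC 0.05, within-patient correlation 0.3), the on/off term estimates:

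| Build-up | Truth | On/off estimate |
|---|---|---|
| 2 rounds | 17.8-18.2 | 12.1 |
| 3 rounds | 15.6-16.4 | 6.9 |
| 4 rounds | 13.3-14.5 | 3.6 |

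**The case against.** The strongest reply is that VI.c is brief, not wrong. It states the intention to handle time, cites a stepped-wedge methods source and nowhere says that time will be left out. That stands: a reader might infer that the plan rules out period terms, and the text does not support this. The reply does not close the gap, because the reference is attached to the design sentence, while the model sentence names a different adjustment.

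Other objections stand in part.

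- *Drift is assumed.* The registry patients were already on treatment in monthly care, and no adherence threshold governs entry, so regression to the mean is not an argument for the primary outcome.
- *The 76-80% rate mixes two problems.* A reader might put all of it down to drift. Without drift, the uncorrected sandwich already rejects in 10-11% of trials, and VI.c does not say whether its sandwich is corrected. The corrected comparison, 68-72% against about 4%, isolates time better.
- *Round effects are not the only remedy.* Wave-specific linear trends also remove linear drift, with an SE of 3.6-3.8 against 4.1 points (eight rounds, ICC 0.05, within-patient correlation 0.3). They protect only if drift is linear.
- *The remedy has its own bias.* Under a four-round build-up without drift, a model with no time terms gives 12.8-14.0, much nearer the truth than 3.6. This is a real trade-off, and the reason for a time-since-rollout model.
- *The Schema is an attachment not available here.* Rollout timing was therefore assumed, but step 3 does not depend on which schedule applies.

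**Conclusion.** The point holds as a gap in specification, rated should-fix. The stated protection against time-related bias depends on terms that VI.c does not state. A model following its wording literally would move about 55-57% of any linear change over 21 months into the programme effect. That share assumes eight rounds, one rollout per round and an exchangeable working correlation. It is slightly lower under independence, and lower again if the working correlation decays over time.

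A reader might go further and conclude that the trial's result will be biased. The documents do not support that: it needs both the omission of time terms and a real drift, and they establish neither. A reader might also take the paired t-test in VI.d as the planned depression analysis. It appears only in the power calculation. That calculation, and the eight-versus-five count of periods, are separate points to reconcile.

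**What to change.** State in VI.c that the primary adherence model and the quantitative secondary models include:

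- fixed survey-round effects specific to each wave (A-D, E-H);
- a time-varying exposure indicator based on each community's actual rollout date;
- a small-sample-corrected sandwich variance, such as Mancl-DeRouen, in place of the plain one. With eight communities and period terms, the uncorrected version rejects a true null in 17-18% of trials, against about 4-5% with the correction.

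Name the on/off exposure effect as primary. Pre-specify a time-since-rollout model (first, second, third-or-later exposed round) as a sensitivity analysis.

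The cost is mainly wording. Rollout dates must be on record; the forms are not available here, so whether they already are cannot be judged. The statistical price is the larger SE and the power figures in step 6. Power can fall below the stated 80% with t-based inference, community autocorrelation of 0.8 or only five rounds. The on/off term will understate an effect that builds up. The time-since-rollout model is unbiased for build-up over two or three rounds, with an SE of 5.4-5.6 against 4.1 points, but still understates a four-round build-up (10.4-11.0 against 13.3-14.5).
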